#### **6.4. Lost to follow-up:**

All reasonable efforts must be made to locate subjects to determine and report their ongoing status. This includes follow-up with persons authorized by the subject as noted above. Lost to follow-up is defined by the inability to reach the subject after a minimum of 2 documented phone calls, faxes, or e-mails as well as lack of response by the subject to 1 registered mail letter. All attempts should be documented in the subject’s medical records. If it is determined that the subject has died, the site will use permissible local methods to obtain the date and cause of death. If the investigator’s use of a third-party representative to assist in the follow-up portion of the study has been included in the subject’s informed consent, then the investigator may use a sponsor-retained third-party representative to assist site staff with obtaining the subject’s contact information or other public vital status data necessary to complete the follow-up portion of the study. The site staff and representative will consult publicly available sources, such as public health registries and databases, in order to obtain updated contact information. If, after all attempts, the subject remains lost to follow-up, then the last-known-alive date as determined by the investigator should be reported and documented in the subject’s medical records.

### **7. ASSESSMENTS**

Every effort should be made to ensure that the protocol-required tests and procedures are completed as described. However, it is anticipated that from time to time there may be circumstances outside of the control of the investigator that may make it unfeasible to perform the test. In these cases the investigator will take all steps necessary to ensure the safety and well-being of the subject. When a protocol-required test cannot be performed, the investigator will document the reason for this and any corrective and preventive actions that he or she has taken to ensure that normal processes are adhered to as soon as possible. The study team will be informed of these incidents in a timely fashion.

Consistent with the institutional guidelines, a topical anesthetic (eg, topical lidocaine) may be administered to subjects prior to the blood draw.

#### **7.1. Blood Volume**

The total blood volume per month will not exceed approximately 40 mL.

The following chart provides estimates of the approximate blood volume collected by visit.

Period	Visit	Total Volume (mL) At Each Visit
Year 1	Screening	40
	Week 13	10
	Week 25	14
	Week 37	10
	Week 49	40
	All other visits (9 additional visits)	10*
	Total Volume Year 1	204
Year 2-4	Week 61, 109, 157	10
	Week 73, 121, 169	22
	Week 85, 133, 181	10
	Week 97, 145, 193	40
	All other visits (9 additional visits per year)	10*
	Total Volume Year 2, 3, 4	172
	Early Withdrawal	30

\*Standard hematology/chemistry and routine safety bloods as required.

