**Study Flowchart: Year 2, 3 and 4 and Early Withdrawal**

	Year 2,3,4 and Early Withdrawal													Early Withdrawal
	14 26, 38	15, 27, 39	16 28, 40	17, 29, 41	18, 30, 42	19, 31, 43	20, 32, 44	21, 33, 45	22, 34, 46	23, 35, 47	24, 36, 48	25, 37, 49		
Visit Number a	14 26, 38	15, 27, 39	16 28, 40	17, 29, 41	18, 30, 42	19, 31, 43	20, 32, 44	21, 33, 45	22, 34, 46	23, 35, 47	24, 36, 48	25, 37, 49		
Study Week a	53, 101, 149	57, 105, 153	61, 109, 157	65, 113, 161	69 117, 165	73 121, 169	77 125, 173	81 129, 177	85 133, 181	89 137, 185	93 141, 189	97 145, 193		
Study Day a	365, 701, 1037	393, 729, 1065	421, 757, 1093	449, 785, 1121	477, 813, 1149	505 841, 1177	533, 869, 1205	561, 897, 1233	589, 925, 1261	617, 953, 1289	645, 981, 1317	673, 1009, 1345		
Visit Window	± 3 days													
Safety Assessments/Questionnaire														
Physical Examination b			X			X			X			X		X
Tanner Stage and Testicular Volume c						X							X	X
Height d						X							X	X
Weight e	X	→	→	→	→	→	→	→	→	→	→	→	X	X
Vital Signs f				X		X			X				X	X
Single ECG			X			X			X				X	X
Cardiac MRI (or Echocardiogram) g													X	X
Clinical Laboratory Tests h			X			X			X				X	X
Serum Ferritin, Serum Iron, TIBC, % Transferrin Saturation h			X			X			X				X	X
Hormones (LH, FSH, T4, TSH, androstenedione, testosterone) c,d						X							X	X
Fecal Occult Blood i			X			X			X				X	X
Clinical Outcomes Assessments (Completed by Caregiver)														
PODCI Questionnaire j							X						X	X
C-SSRS k						X			X				X	X
EQ-5D-3L						X							X	X
HRU						X							X	
ZBI						X							X	X
WPAI-CG						X							X	X
Clinical Outcomes Assessments (Completed by Subject)														
PODCI Questionnaire l	X					X							X	X
EQ-5D-Y	X					X							X	X
Imaging Assessments														

PF-06252616

B5161004

Final Protocol, 08 April 2016

090177e1911f2727\Approved\Approved On: 18-Jun-2019 06:41 (GMT)

Visit Number a	Year 2,3,4 and Early Withdrawal												
	14 26, 38	15, 27, 39	16 28, 40	17, 29, 41	18, 30, 42	19, 31, 43	20, 32, 44	21, 33, 45	22, 34, 46	23, 35, 47	24, 36, 48	25, 37, 49	Early Withdrawal
Study Week a	53, 101, 149	57, 105, 153	61, 109, 157	65, 113, 161	69 117, 165	73, 121, 169	77, 125, 173	81, 129, 177	85, 133, 181	89, 137, 185	93, 141, 189	97, 145, 193	

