Study Day a	365, 701, 1037	393, 729, 1065	421, 757, 1093	449, 785, 1121	477, 813, 1149	505, 841, 1177	533, 869, 1205	561, 897, 1233	589, 925, 1261	617, 953, 1289	645, 981, 1317	673, 1009, 1345	
Visit Window	± 3 days												
MRI-Liver						X						X	X
DXA-Spine												X	X
DXA-Whole Body												X	X
X-ray (hand and wrist) c												X	X
Functional Assessments													
Ambulatory status m	X	→	→	→	→	→	→	→	→	→	→	X	X
PFTs						X						X	X
4 Stair Climb n					X							X	X
Northstar Ambulatory Assessment n					X							X	X
Range of Motion					X							X	X
Strength Assessment					X							X	X
PUL					X							X	X
6MWT n					X							X	X
Investigational Product Administration													
Investigational Product administration o	X	X	X	X	X	X	X	X	X	X	X		
PK/Immunogenicity													
PK sample p						X						X	X
Immunogenicity					X							X	X
Biobanking Sample (Group 1 and Group 2 Biomarkers)												X	
Infusion Site Reaction monitoring	X	→	→	→	→	→	→	→	→	→	→	→	X
Adverse event monitoring	X	→	→	→	→	→	→	→	→	→	→	→	X
Concomitant medication	X	→	→	→	→	→	→	→	→	→	→	→	X

Abbreviations: → = ongoing/continuous monitoring; 6MWT=Six minute walk test; C-SSRS=Columbia Suicide Severity Rating Scale, DXA=Dual-energy x-ray absorptiometry; ECG = electrocardiogram; EQ-5D-3L=EuroQoL 5 Dimensions 3 Levels; EQ-5D-Y=EuroQoL 5 Dimensions - Youth; FSH= Follicle stimulating hormone; HRU=Healthcare Resource Utilization; LH= Luteinizing hormone; MRI=magnetic resonance image; PD=Pharmacodynamics; PFTs = pulmonary function tests; PK=Pharmacokinetics, PODCI=Pediatric Outcomes Data Collection Instrument; PUL=Performance of Upper Limb, T4 =thyroxine; TIBC=Total

Visit Number a	Year 2,3,4 and Early Withdrawal												
	14 26, 38	15, 27, 39	16 28, 40	17, 29, 41	18, 30, 42	19, 31, 43	20, 32, 44	21, 33, 45	22, 34, 46	23, 35, 47	24, 36, 48	25, 37, 49	Early Withdrawal
Study Week a	53, 101, 149	57, 105, 153	61, 109, 157	65, 113, 161	69 117, 165	73, 121, 169	77, 125, 173	81, 129, 177	85, 133, 181	89, 137, 185	93, 141, 189	97, 145, 193	
Study Day a	365, 701, 1037	393, 729, 1065	421, 757, 1093	449, 785, 1121	477, 813, 1149	505, 841, 1177	533, 869, 1205	561, 897, 1233	589, 925, 1261	617, 953, 1289	645, 981, 1317	673, 1009, 1345	
Visit Window	± 3 days												

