### 6.3. Subject Withdrawal

Subjects may withdraw from the study at any time at their own request, or they may be withdrawn at any time at the discretion of the investigator or sponsor for safety or behavioral reasons, or the inability of the subject/caregiver to comply with the protocol-required schedule of study visits or procedures at a given study site. Subjects may be withdrawn from the OLE study should the parent study, B5161002 fail to meet its planned study objectives, is terminated early for other reasons (eg, sponsor decision) or the drug is commercialized. If a subject does not return for a scheduled visit, every effort should be made to contact the subject. All attempts to contact the subject and information received during contact attempts must be documented in the subject's medical records. In any circumstance, every effort should be made to document subject outcome, if possible. The investigator should inquire about the reason for withdrawal, request that the subject to return for a final visit, if applicable, and follow-up with the subject regarding any unresolved AEs.

If the subject withdraws from the study and also withdraws consent for disclosure of future information, no further evaluations should be performed and no additional data should be collected. The sponsor may retain and continue to use any data collected before such withdrawal of consent.

In the event of clinically important treatment-emergent suicidal ideation or suicidal behavior, the subject will be withdrawn from the study and will receive the appropriate medical care. The Investigator will follow up until the subject's condition has stabilized. Additionally, a risk assessment or evaluation of suicide risk will be completed by a child and adolescent mental health provider as part of the psychiatric evaluation and assessment of subject safety. Refer to [Section 7.2.7](#).

Clinically important suicidality includes but is not limited to:

- a. Suicidal behavior (with or without intent of suicide or serious self-harm).
- b. Determination of “yes” on question 4 (Active Suicidal Ideation with Some Intent or Act, Without Specific Plan) for the Suicidal Ideation section of the C-SSRS.

- c. Determination of “yes” on question 5 (Active Suicidal Ideation with Specific Plan and Intent) for the Suicidal Ideation section of the C-SSRS.

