- d. Determination of “yes” on the question of Actual Attempt, Interrupted Attempt, Aborted Attempt, or Preparatory Acts or Behavior for Suicidal Behavior section of C-SSRS.
- e. Acute suicidality to such a degree that precaution against suicide must be exercised.

At the time of withdrawal, procedures outlined in the early withdrawal visit should be performed as detailed in the [Schedule of Activities](#) and [Assessments](#).

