**Biomarker Group 1- Collect annually beginning at screening in current study:**

- **Prep B1.5 (K2 EDTA plasma collection optimized for biomarker/proteomic/metabonomic analysis):** A 2 mL blood biospecimen will be collected.
- **Prep B2.5 (serum collection optimized for biomarker/ proteomics/metabonomic analysis):** A 2.5 mL blood biospecimen will be collected.

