**Biomarker Group 2- Collect annually beginning at screening in current study:**

- **Prep R1 (PAXGene whole blood collection optimized for RNA analysis):** A 2.5 mL blood biospecimen will be collected.
- **Prep P4 (Cell-free RNA):** A 10 mL blood biospecimen will be collected.

The banked biospecimens will be collected from all subjects **unless prohibited by local regulations or ethics committee decision**. Detailed collection, processing, storage, and shipment instructions are provided in the central laboratory manual.

It is possible that the use of these biospecimens may result in commercially viable products. Subjects will be advised in the ICD/subject information sheet that they will not be compensated in this event.

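### Protocol Section 7.1 limits blood volume to about 40 mL per month, but its own chart gives 70 mL when an Early Withdrawal visit follows a 40 mL visit within 4 weeks, and its Years 2-4 total counts one visit too many

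*Protocol*

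**What the plan says.** Section 7.1 (Blood Volume) gives the limit: "The total blood volume per month will not exceed approximately 40 mL". It then introduces a chart of estimated volumes by visit:

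- Year 1: Screening 40 mL; Week 13, 10 mL; Week 25, 14 mL; Week 37, 10 mL; Week 49, 40 mL; nine other visits at 10 mL each, as required; total 204 mL.
- Years 2-4, per year: 10 mL (Weeks 61, 109, 157); 22 mL (Weeks 73, 121, 169); 10 mL (Weeks 85, 133, 181); 40 mL (Weeks 97, 145, 193); then "All other visits (9 additional visits per year", at 10 mL each as required; total 172 mL.
- Early Withdrawal: 30 mL.

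On withdrawal, Section 6.3 says "Subjects may withdraw from the study at any time at their own request", and that at that time the "procedures outlined in the early withdrawal visit should be performed as detailed in the" Schedule of Activities and Assessments. The Early Withdrawal column of the schedule marks clinical laboratory tests, iron studies, hormones, PK and immunogenicity. The row "Biobanking Sample (Group 1 and Group 2 Biomarkers" is marked at the year-end visit but not at Early Withdrawal.

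**The concern.** The limit covers all blood taken in a month, and scheduled visits are 4 weeks apart. Early Withdrawal is an additional visit that can fall at any point between them. If it comes soon after one of the large draws, two chart entries land in the same 4-week period and their sum is well above the stated limit.

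The protocol does not say which instruction gives way. Section 6.3 has no minimum interval from a previous draw and no waiver for tests just done. Section 7 asks for every effort to complete the required tests and provides for omission only where circumstances outside the investigator's control make a test unfeasible. A site that respects the 40 mL limit has no rule on what to leave out, and a site that follows the withdrawal column exceeds the limit. At stake is a stated safeguard on blood taken from children, not any statistical result.

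**Working it through.** **1. The plan's own totals.**

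- Year 1: 40 + 10 + 14 + 10 + 40 + 9 × 10 = 204 mL. This matches the chart.
- Years 2-4, with the stated nine other visits: 10 + 22 + 10 + 40 + 9 × 10 = 172 mL. This matches the chart's addition.
- The largest single visit is 40 mL, which agrees with the limit if it is read visit by visit.

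**2. Early Withdrawal after a 40 mL visit, using the chart's figures.**

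- The next scheduled visit after each year-end visit is 28 days later: Day 337 to 365, Day 673 to 701, and Day 1009 to 1037. A withdrawal visit before or at the next visit is therefore within 4 weeks of the 40 mL draw.
- Total: 40 + 30 = 70 mL; 70 / 40 = 175% of the limit.
- The same sum applies after Screening if the withdrawal visit falls within 4 weeks of that draw. Week 193 is left out because it is the last scheduled visit.

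**3. Does a smaller withdrawal draw rescue the limit?** Section 7.3.1 gives the biobanking volumes. In Group 1, one tube is described as "A 2 mL blood biospecimen will be collected" and the other is 2.5 mL. In Group 2, one tube is 2.5 mL and the other is described as "A 10 mL blood biospecimen will be collected".

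- Biobanking: 2 + 2.5 + 2.5 + 10 = 17 mL.
- Year-end without biobanking: 40 - 17 = 23 mL.
- If Early Withdrawal uses the same tubes as year-end apart from biobanking (an assumption), the total is 40 + 23 = 63 mL, or 63 / 40 = 158%.

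The limit is exceeded either way. The 23 mL figure is an inference from the schedule and does not replace the printed 30 mL.

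**4. Smaller overlaps, for scale.** After the Years 2-4 mid-year visit the sum is 22 + 30 = 52 mL on the chart, or 22 + 23 = 45 mL by components. After Week 25 it is 14 + 30 = 44 or 14 + 23 = 37 mL. These are marginal against an approximate limit and are not relied on.

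**5. The Years 2-4 visit count.** The "Study Flowchart: Year 2, 3 and 4 and Early Withdrawal" has 12 visits per year. The chart names 4 of them, so 12 - 4 = 8 remain (in Year 2: Weeks 53, 57, 65, 69, 77, 81, 89 and 93). The total is 10 + 22 + 10 + 40 + 8 × 10 = 162 mL, which is 10 mL below the printed 172. Nine is correct for Year 1, where 13 visits less 4 named leave 9.

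**The case against.** The best defence is that Section 7.1 speaks of an approximate limit and calls its chart an estimate. Planned visits are 4-weekly and none exceeds 40 mL. Read as a ceiling per monthly visit, the sentence and the chart agree, and the 70 mL is a sum the chart never prints. On that view the protocol lacks a contingency instruction and contains no wrong number. This stands in part: the scheduled visits do keep the limit on that reading, and the conflict needs an unplanned visit. But even if a month means the 4-week visit cycle, an Early Withdrawal visit inside the cycle adds a second draw, and wording that allows for rounding does not cover a 75% excess.

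A second defence is that the protocol leaves room to comply. The limit is worded as firm and the withdrawal procedures as expected, Section 6.3 asks for a final visit only if applicable, and hormone testing stops being mandatory at Tanner Stage V. A careful site could reduce the draw. That also stands, but no text tells it to do so or says which tests to drop.

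A reader might go further and infer that the 30 mL entry is itself wrong because the components come to about 23 mL. The documents do not establish this. The estimate rests on a blank table cell and on assumed tube volumes, and 30 mL is also what remains if only the 10 mL tube is left out (40 - 10 = 30). A reader might also infer that year-end is the only case affected; Screening followed by Early Withdrawal gives the same 70 mL on the same reading.

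**Conclusion.** The point holds as a minor one. By the chart's own figures, Early Withdrawal within 4 weeks of Screening or of Week 49, 97 or 145 gives 70 mL against a limit of about 40 mL, and nothing waives the repeat draws. The size rests on the chart's two entries and on taking a month as about 4 weeks. The component estimate of about 63 mL points the same way but is only an inference.

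The visit miscount needs no assumption: the Years 2-4 total should be 162 mL per year. The printed figure errs on the high side.

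It would be tempting to conclude that the study plans to overdraw children routinely, or that 70 mL is unsafe. The documents support neither. The overlap arises only on withdrawal, the protocol gives no withdrawal rate from which to estimate its frequency, and it gives no volume limit per kilogram against which to judge 70 mL. No endpoint or analysis is affected.

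**What to change.** 1. Add a footnote to the Early Withdrawal column of the Schedule of Activities: blood tests already drawn at a 40 mL visit within the preceding 4 weeks are not repeated unless clinically indicated, and any repeat is limited to the minimum safety sample, about 10 mL on the chart.
2. Reword Section 7.1 so that the 40 mL limit applies to scheduled visits, and name this one exception with its maximum: 40 + 10 = about 50 mL. This is better than rewriting the limit to permit 70 mL. Tying the limit to scheduled visits also settles the undefined month: a year-end visit and the next routine visit 28 days later can otherwise add to 40 + 10 = 50 mL with no withdrawal at all.
3. In the Years 2-4 rows of the chart, change 9 other visits per year to 8 and 172 mL to 162 mL.

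The cost is one footnote, a reworded sentence and two corrected entries. The downside is that some non-core withdrawal values, including PK and anti-drug antibody results if not redrawn, may be up to 4 weeks old. At Week 49 the PK sample is also taken before that visit's infusion, so it would not reflect that dose. Taking no blood at all at such a withdrawal would keep the total at 40 mL but would give up the safety sample; the allowance for a clinically indicated repeat is the reason for stating 50 mL.

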## 7.2. Safety

### 7.2.1. Clinical Laboratory

The following safety laboratory tests will be performed at times defined in the [Schedule of Activities](#) section of this protocol. Unscheduled clinical labs may be obtained at any time during the study to assess any perceived safety concerns.

## Laboratory Tests

Hematology	Chemistry	Urinalysis	Other	
Hemoglobin Hematocrit RBC count Platelet count WBC count (and morphology as applicable) Total neutrophils (Abs) Absolute neutrophils (ANC) Eosinophils (Abs) Monocytes (Abs) Basophils (Abs) Lymphocytes (Abs)	BUN Creatinine Glucose Calcium Sodium Potassium Chloride Total CO2 (Bicarbonate) AST, ALT Total Bilirubin Alkaline phosphatase Uric acid Albumin Total protein Serum Phosphorus	pH Glucose (qual) Protein (qual) Blood (qual) Ketones Nitrites Leukocyte esterase Microscopy a	GGT GLDH PT INR aPTT Creatine kinase Amylase Cardiac Troponin I Serum Ferritin c Serum Iron c Total Iron Binding c Capacity (TIBC) c Unsaturated Binding capacity c , % Transferrin Saturation c Hormones (LH, FSH, T4 (total and free), TSH, androstenedione, testosterone) d	Fecal Occult Blood
	Additional Testsb			
	AST, ALT (repeat) Total bilirubin (repeat) Albumin (repeat) Alkaline phosphatase (repeat) Direct bilirubin Indirect bilirubin Creatine kinase GGT GLDH PT INR			

a. Only if urine is positive for blood, protein, nitrites or leukocyte esterase.

b. Additional testing for potential Hy's Law cases only.

c. Following an 8 hour overnight fast.

d. Collect blood in the morning for hormone testing.

### 7.2.2. Physical Examinations/Nose and Throat Exam

Physical examinations may be conducted by a physician, trained physician's assistant, or nurse practitioner as acceptable according to local regulation. The physical examination will include head, ears, eyes, nose, mouth, skin, heart and lung examinations, lymph nodes, gastrointestinal, musculoskeletal, and neurological systems. A targeted nose and throat

mucosal exam will be performed according to the [Schedule of Activities](#) to monitor for any signs of mucosal telangiectasias. If the examination status is abnormal, the investigator will be asked to determine whether the abnormality is “clinically significant”, and if so, document as an AE.

#### **7.2.3. Tanner Stage and Testicular Volume**

Tanner Staging will be performed according to the [Schedule of Activities](#) to monitor for signs of accelerated sexual development. The physical changes in pubertal development (genital and pubic hair growth) will be assessed using the system described by [Marshall and Tanner \(1970\)](#). In addition to the Tanner staging, a measurement of testicular size (volume) using orchidometer beads will be documented. If a subject reaches a Tanner Stage V during the conduct of the study, further Tanner Staging, Testicular Volume, hormone testing and x-rays will no longer be mandatory.

#### **7.2.4. Vitals**

Supine blood pressure, pulse rate, respiratory rate and temperature will be measured at times specified in [Schedule of Activities](#) section of this protocol. Unscheduled collection times will be permitted, as necessary, to ensure appropriate collection of safety data.

Supine blood pressure will be measured with the subject’s arm supported at the level of the heart, and recorded to the nearest mm Hg after at least 5 minutes of rest.

The use of automated devices for measuring BP and pulse rate are acceptable, although, when done manually, pulse rate will be measured in the brachial/radial artery for at least 30 seconds.

#### **7.2.5. Electrocardiogram (ECG)**

ECGs should be collected at times specified in the [Schedule of Activities](#) section of this protocol.

All scheduled ECGs should be performed after the subject has rested quietly for at least 10 minutes in a supine position.

Single 12-lead ECGs will be obtained; the average of the triplicate ECG measurements collected at Week 97 from Study B5161002, will serve as each subject’s time-controlled baseline QTc value.

The QTc interval should be recorded using the QTcF (QTc Fridericia) value in milliseconds. In the event that the equipment is not able to provide the QTcF, the formula below will be used to calculate.

Formula =  $QT/((60/HR)^{(1/3)})$

To ensure safety of the subjects, a qualified individual at the investigator site will make comparisons to baseline measurements. If the QTcF interval is increased by  $\geq 45$  msec from

the baseline, or an absolute QTcF value is  $\geq 500$  msec for any scheduled ECG, then 2 additional ECGs will be collected, approximately 2-4 minutes apart, to confirm the original measurement.

If the average of QTcF values from the triplicate measurements remains above the threshold value ( $\geq 45$  msec from the baseline; or is  $\geq 500$  msec), then a single ECG must be repeated at least hourly until QTcF values from 2 successive ECGs fall below the threshold value that triggered the repeat measurement.

If QTcF values remain  $\geq 500$  msec (or  $\geq 45$  msec from the baseline) for greater than 4 hours (or sooner at the discretion of the investigator); or QTcF intervals get progressively longer, the subject should undergo continuous ECG monitoring. A cardiologist should be consulted if QTcF intervals do not return to less than 500 msec (or to  $< 45$  msec above the baseline) after 8 hours of monitoring (or sooner at the discretion of the investigator).

In some cases, it may be appropriate to repeat abnormal ECGs to rule out improper lead placement as contributing to the ECG abnormality. It is important that leads are placed in the same positions each time in order to achieve precise ECG recordings. If a machine-read QTcF value is prolonged, as defined above, repeat measurements may not be necessary if a qualified physician's interpretation determines that the QTcF values are in the acceptable range.

